7.7. Special Situations Reports

7.7.1. Definitions of Special Situations

Special situation reports include all reports of medication error, abuse, misuse, overdose, reports of adverse events associated with product complaints, and pregnancy reports regardless of an associated AE.

Medication error is any unintentional error in the prescribing, dispensing, or administration of a medicinal product while in the control of the health care provider, participant, or consumer.

Abuse is defined as persistent or sporadic intentional excessive use of a medicinal product by a participant.

Misuse is defined as any intentional and inappropriate use of a medicinal product that is not in accordance with the protocol instructions or the local prescribing information.

An overdose is defined as an accidental or intentional administration of a quantity of a medicinal product given per administration or cumulatively which is above the maximum recommended dose as per protocol or in the product labelling (as it applies to the daily dose of the participant in question). In cases of a discrepancy in drug accountability, overdose will be established only when it is clear that the participant has taken the excess dose(s). Overdose cannot be established when the participant cannot account for the discrepancy except in cases in which the investigator has reason to suspect that the participant has taken the additional dose(s).

Product complaint is defined as complaints arising from potential deviations in the manufacture, packaging, or distribution of the medicinal product.

Occupational exposure is defined as exposure to a medicinal product as a result of one's professional or non-professional occupation.

7.7.2. Instructions for Reporting Special Situations

7.7.2.1. Instructions for Reporting Pregnancies

The investigator should report pregnancies in female study participants that are identified after initiation of study medication and throughout the study, including the post study drug follow-up period, to Gilead PVE using the pregnancy report form within 24 hours of becoming aware of the pregnancy.

Refer to Section 7.3 and the eCRF completion guidelines for full instructions on the mechanism of pregnancy reporting.

The pregnancy itself is not considered an AE nor is an induced elective abortion to terminate a pregnancy without medical reasons.

Any premature termination of pregnancy (eg, a spontaneous abortion, an induced therapeutic abortion due to complications or other medical reasons) must be reported within 24 hours as an SAE. The underlying medical reason for this procedure should be recorded as the AE term.

A spontaneous abortion is always considered to be an SAE and will be reported as described in Section 7.3. Furthermore, any SAE occurring as an adverse pregnancy outcome post study must be reported to Gilead PVE.

Any complications during pregnancy and the outcome should be reported to Gilead PVE using the pregnancy outcome report form. If the end of the pregnancy occurs after the study has been completed, the outcome should be reported directly to Gilead PVE. Gilead PVE contact information is as follows:

Email: PPD and Fax: PPD

Refer to Appendix 6 for Pregnancy Precautions, Definition for Persons of Childbearing Potential, and Contraceptive Requirements.

7.7.2.2. Reporting Other Special Situations

All other special situation reports must be reported on the special situations report form and forwarded to Gilead PVE within 24 hours of the investigator becoming aware of the situation. These reports must consist of situations that involve study IMP and/or Gilead concomitant medications, but do not apply to non-Gilead concomitant medications.

Special situations involving non-Gilead concomitant medications do not need to be reported on the special situations report form; however, for special situations that result in AEs due to a non-Gilead concomitant medication, the AE should be reported on the AE form.

Any inappropriate use of concomitant medications prohibited by this protocol should not be reported as “misuse,” but may be more appropriately documented as a protocol deviation.

Refer to Section 7.3 and the eCRF completion guidelines for full instructions on the mechanism of special situations reporting.

All clinical sequelae in relation to these special situation reports will be reported as AEs or SAEs at the same time using the AE eCRF and/or the SAE report form. Details of the symptoms and signs, clinical management, and outcome will be reported, when available.

8. STATISTICAL CONSIDERATIONS

8.1. Analysis Objectives and Endpoints

8.1.1. Analysis Objectives

The primary objective of this study is:

- To evaluate the efficacy of switching from a regimen of 2 NRTIs and a third agent to fixed dose combination (FDC) of bictegravir/emtricitabine/tenofovir alafenamide (B/F/TAF) versus continuing their baseline regimen in HIV-infected, virologically suppressed African American participants as determined by the proportion of participants with HIV-1 RNA ≥ 50 copies/mL at Week 24

The secondary objectives of this study are:

- To evaluate the efficacy of switching to FDC of B/F/TAF from a regimen of 2 NRTIs and a third agent as determined by the proportion of participants with HIV-1 RNA ≥ 50 copies/mL at Week 48
- To evaluate the efficacy, safety, and tolerability of switching to FDC of B/F/TAF from a regimen of 2 NRTIs and a third agent in HIV-infected, virologically suppressed African American participants through Week 48

8.1.2. Primary Endpoint

The primary efficacy endpoint is:

- The proportion of participants with HIV-1 RNA ≥ 50 copies/mL at Week 24 as defined by the US FDA-defined snapshot algorithm

8.1.3. Secondary Endpoint

The secondary efficacy endpoints are:

- The proportion of participants with HIV-1 RNA ≥ 50 copies/mL at Week 48 as defined by the US FDA-defined snapshot algorithm
- The proportion of participants with HIV-1 RNA < 50 copies/mL at Week 24 and 48 as defined by the US FDA-defined snapshot algorithm
- The change from baseline in CD4+ cell count at Weeks 24 and 48.

8.2. Analysis Conventions

8.2.1. Analysis Sets

8.2.1.1. All Randomized

The randomized analysis set includes all participants who are randomized into the study. This is the primary analysis set for by-participant listings.

8.2.1.2. Efficacy

8.2.1.2.1. Full Analysis Set

The primary analysis set for efficacy analyses is defined as the full analysis set (FAS), which will include all participants who (1) are randomized into the study, (2) have received at least 1 dose of study treatment, (3) have at least 1 post baseline HIV-1 RNA result while on study treatment, and (4) do not have pre-existing resistance-associated mutations. Participants will be grouped according to the treatment to which they were randomized.

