4.2. Inclusion Criteria

Participants must meet all of the following inclusion criteria to be eligible for participation in this study.

- 1) The ability to understand and sign a written informed consent form, which must be obtained prior to initiation of study procedures
- 2) Age \geq 18 years
- 3) Self-describes as Black, African American, or mixed race including Black
- 4) Currently receiving an ARV regimen other than FDC of B/F/TAF that consists of any two NRTIs + allowed 3rd agent for \geq 6 months
 - a) Allowed 3rd agents include any FDA-approved INSTI, with the exception of bictegravir, any FDA-approved NNRTI with the exception of etravirine, and FDA-approved PI or the CCR5 antagonist, maraviroc
 - b) If the baseline 3rd agent is dolutegravir, dosing other than 50 mg once daily is excluded
 - c) Baseline regimens containing investigational drugs or $>$ 2 classes of ARVs are not permitted, with the exception of the pharmacologic enhancers cobicistat (taken with elvitegravir or a PI), or ritonavir (taken with a PI)
- 5) Have no documented or suspected resistance to INSTIs and no history of virologic failure on an INSTI containing regimen (2 consecutive HIV-1 RNA \geq 50 copies/mL after achieving $<$ 50 copies/mL while on an INSTI-containing regimen)
- 6) History of 1-2 thymidine analogue mutations (TAMs; M41L, D67N, K70R, L210W, T215F/Y, and K219Q/E/N/R), M184V/I, and RT substitutions not described in exclusion criterion 1 are allowed. Any NNRTI or PI resistance mutations are allowed.
- 7) Documented plasma HIV-1 RNA $<$ 50 copies/mL during treatment with the baseline regimen for a minimum period of 6 months and at least the last two HIV-1 RNA measurements prior to the Screening visit
 - a) Must include one or more HIV-1RNA tests within the 12 months prior to screening

- 8) Willingness to wait approximately 6 months before switching from current ARVs
- 9) HIV-1 RNA levels < 50 copies/mL at Screening
- 10) Estimated glomerular filtration rate (eGFR) \geq 50 mL/min according to the Cockcroft-Gault (C-G) formula {[Cockcroft 1976](#)}:
- Male:
$$\frac{(140 - \text{age in years}) \times (\text{wt in kg})}{72 \times (\text{serum creatinine in mg/dL})} = \text{CLcr (mL/min)}$$
$$\frac{(140 - \text{age in years}) \times (\text{wt in kg})}{72 \times (\text{serum creatinine in umol/L}) \times 0.6786} = \text{CLcr (mL/sec)}$$
- Female:

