4.3. Exclusion Criteria

Participants who meet *any* of the following exclusion criteria are not to be enrolled in this study.

- 1) History of 3 or more TAMs (M41L, D67N, K70R, L210W, T215F/Y, and K219Q/E/N/R), T69-insertions, or K65R/E/N in RT will be excluded
- 2) No desire to switch from current ARVs
- 3) An opportunistic illness indicative of stage 3 HIV diagnosed within the 30 days prior to screening (refer to [Appendix 5](#))
- 4) Participants experiencing decompensated cirrhosis (e.g., ascites, encephalopathy, or variceal bleeding)
- 5) Have been treated with immunosuppressant therapies or chemotherapeutic agents within 3 months of study screening, or expected to receive these agents or systemic steroids during the study (eg, corticosteroids, immunoglobulins, and other immune- or cytokine-based therapies)
- 6) Malignancy within 5 years of screening other than cutaneous Kaposi's sarcoma, completely resected non-melanoma skin cancer (basal cell carcinoma or non-invasive cutaneous squamous carcinoma), or completely resected carcinoma in-situ of the cervix (CIN 3) or anus (AIN 3). A prior malignancy treated with curative therapy and for which there has been no evidence of disease for at least five years prior to screening is allowed.
- 7) Current alcohol or substance use judged by the Investigator to potentially interfere with participant study compliance
- 8) Active, serious infections (other than HIV-1 infection) requiring antibiotic or antifungal therapy within 30 days prior to Day 1
- 9) Participation in any other clinical trial, including observational studies, without prior approval from the sponsor is prohibited while participating in this trial
- 10) Any other clinical condition or prior therapy that, in the opinion of the Investigator, would make the participant unsuitable for the study or unable to comply with the dosing requirements
- 11) Known hypersensitivity to FDC of B/F/TAF tablets, their metabolites, or formulation excipient
- 12) Females who are pregnant (as confirmed by positive serum pregnancy test)
- 13) Females who are breastfeeding
- 14) Participants receiving ongoing therapy with any of the following medications in the table below, including drugs not to be used with FDC of B/F/TAF

Drug Class	Agents Disallowed*
Antiarrhythmic Agent	Dofetilide
Anticonvulsants	Phenobarbital, Phenytoin, Carbamazepine, Oxcarbazepine
Antimycobacterials	Rifampin, Rifapentine, Rifabutin

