6.2. Pretreatment Assessments

6.2.1. Screening Visit

Participants will be screened within 30 days before Day 1 to determine eligibility for participation in the study. The following will be performed and documented at screening:

- Obtain written informed consent(s)
- Obtain demographic information, including gender at birth, sexual orientation, and gender identity
- Obtain screening number in IWRS
- Obtain medical history including history of HIV-1 disease-related events, and prior medications within 30 days of the screening visit
- If available, obtain documentation of historical genotype(s) (**not required for entry to study**)
- Complete physical examination (urogenital/anorectal exams will be performed at the discretion of the Investigator)
- 12-lead ECG performed supine
- Height
- Vital signs measurement (blood pressure, pulse, respiration rate, and temperature), including weight
- Obtain blood and urine samples as described in Sections [6.9.1](#) and [6.9.2](#)
- Review concomitant medications
- Record any SAEs and all AEs related to protocol mandated procedures occurring after signing of the consent form

Participants meeting all of the inclusion criteria, and none of the exclusion criteria, will return to the clinic within 30 days after screening for the Day 1 Visit. Participants randomized to Treatment Group 1 must continue to take their prior treatment regimen up until the day before their scheduled Day 1 visit. Participants randomized to Treatment Group 2 will continue to take their prior treatment regimen until they switch to FDC of B/F/TAF at Week 24.

From the time of obtaining informed consent through the first administration of study treatment, record all SAEs, as well as any AEs related to protocol-mandated procedures on the adverse events eCRF. All other untoward medical occurrences observed during the screening period, including exacerbation or changes in medical history are to be captured on the medical history eCRF. See Section 7 Adverse Events and Toxicity Management for additional details.

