- b. If the HIV-1 RNA is < 50 copies/mL then no further action is required. If the HIV-1 RNA is between 50 and 200 copies/mL, a reflex HIV-1 RNA repeat test will be conducted on stored plasma if available. If the repeat result is < 50 copies/mL, then no further action is required. If the repeat result is between 50 and 200 copies/mL this is protocol defined confirmed virologic failure and the Medical Monitor should be consulted. If the repeat result is ≥ 200 copies/mL, then a Genotype and Phenotype test will be ordered.
- c. If virologic rebound is confirmed and the last HIV-1 RNA is ≥ 200 copies/mL, the HIV-1 genotype and phenotype (reverse transcriptase, protease and integrase) will be analyzed. If the genotype and phenotype assay fails, Investigator reviews study treatment continuation/discontinuation options and discuss with the Medical Monitor prior to study treatment discontinuation.
- d. If no new resistance to study treatment is detected, HIV-1 RNA will be repeated 2 – 3 weeks later. Investigator reviews study treatment continuation/discontinuation options and discuss with the Medical Monitor prior to study treatment discontinuation. The participant will remain in the study.
- e. A new ARV regimen may be configured, at the Investigator's discretion and the participant will remain in the study.

6.13.2. Participants with HIV-1 RNA ≥ 50 copies/mL at Study Drug Discontinuation, Week 24, or Week 48

Participants with HIV-1 RNA ≥ 50 copies/mL at study drug discontinuation, last visit, or last Week 24 or Week 48 result will be considered virologic failures. Participants with HIV-1 RNA ≥ 50 copies/mL at Week 24 or Week 48 will be asked to return for an unscheduled visit within the visit window for a retest.

Participants with HIV-1 RNA ≥ 200 copies/mL at study drug discontinuation, last visit, or Week 24 or Week 48 visit, will also have resistance testing conducted.

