8.2.1.2.2. Per-Protocol (PP) Analysis Set for anti-HIV Efficacy Analysis

The secondary analysis set for anti-HIV efficacy analyses is defined as the per-protocol (PP) analysis set for anti-HIV efficacy analysis, which will include all participants who (1) are randomized into the study, (2) have received at least 1 dose of study treatment, and (3) have not committed any major protocol violation, including the violation of key entry criteria. Participants will be grouped according to the treatment they actually received.

Participants meeting any of the following criteria will be excluded from the Week 24 PP analysis set for anti-HIV efficacy analysis:

- Participants who do not have on-treatment HIV-1 RNA in the Week 24 analysis window, except when missing due to discontinuation of study treatment for lack of efficacy.
- Participants who meet the exclusion criterion for receiving ongoing therapy with any of the medications listed in the table in protocol Section 4.3 including drugs not to be used with bictegravir.
- Nonadherence to study treatment: participants with adherence rate for active study treatment up to the Week 24 Visit below the 2.5th percentile
- Participants who do not meet the inclusion criteria for history of 3 or more TAMs (M41L, D67N, K70R, L210W, T215F/Y, and K219Q/E/N/R), T69-insertions, or K65R/E/N in RT, including pre-existing mutations that are detected post-baseline

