8.5. Efficacy Analysis

8.5.1. Primary Analysis

The primary analysis will consist of a non-inferiority test of switching to FDC of B/F/TAF versus SBR, with respect to the proportion of participants with HIV-1 RNA \geq 50 copies/mL at Week 24, as defined by the US FDA-defined snapshot algorithm. The primary analysis of the efficacy endpoint will be based on the FAS.

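### The primary analysis set bars resistance mutations without naming a drug class or data source, so as written it drops participants whom the entry criteria admit

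*Protocol*

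**What the plan says.** Protocol 8.5.1 fixes the primary population: "The primary analysis of the efficacy endpoint will be based on the FAS". Protocol 8.2.1.2.1 builds that set from randomized participants with at least one dose who also "3) have at least 1 post baseline HIV-1 RNA result while on study treatment, and (4) do not have pre-existing resistance-associated mutations". No mutation list, drug class or sample is named.

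Inclusion criterion 6 (protocol 4.2) admits a history of 1-2 thymidine analogue mutations (TAMs) and continues: "M184V/I, and RT substitutions not described in exclusion criterion 1 are allowed. Any NNRTI or PI resistance mutations are allowed". Exclusion criterion 1 (protocol 4.3) bars a short list only: "History of 3 or more TAMs (M41L, D67N, K70R, L210W, T215F/Y, and K219Q/E/N/R), T69-insertions, or K65R/E/N in RT will be excluded". Inclusion criterion 5 separately bars documented or suspected INSTI resistance.

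The per-protocol (PP) set in 8.2.1.2.2 repeats only the short list. It removes "Participants who do not meet the inclusion criteria for history of 3 or more TAMs", T69 insertions or K65R/E/N, "including pre-existing mutations that are detected post-baseline".

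SAP 3.1.2 defines a B/F/TAF FAS for the final analysis. Its resistance condition is limited to INSTI mutations known from historical data, and it has no post-baseline RNA condition. SAP sections 1 and 6.1.1 say that the primary analysis was described in another SAP and will not be repeated. SAP 6.4 states that no change from the protocol-specified efficacy analyses is planned.

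**The concern.** An FAS is normally the broad set and the PP set the narrow one. Here an eligible, treated participant with M184V can be in the PP set and not in the FAS. If condition (4) is programmed as written, the non-inferiority claim rests on a population narrower than the one the trial set out to enrol, with fewer participants than the power calculation assumes.

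The missing data source is the second problem. Three sources could define a pre-existing mutation, and they cover different people. If genotypes taken after baseline were used, membership of the primary set would depend partly on viraemia during the trial, which is close to the endpoint itself.

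Condition (3) is a lesser issue of the same kind. It excludes on something that happens after randomization in an open-label trial.

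**Working it through.** **Step 1: the mutation rules side by side**

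| Finding in a treated participant | Entry (4.2, 4.3) | FAS condition (4), literal | PP mutation rule |
|---|---|---|---|
| 1-2 TAMs, M184V/I, other permitted RT substitution | admitted | removed | kept |
| any NNRTI or PI mutation | admitted | removed | kept |
| 3 or more TAMs, T69 insertion, K65R/E/N | barred | removed | removed |
| INSTI resistance, documented or suspected | barred | removed if a mutation is known | not listed by name; entry violation |

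The first two rows are the contradiction. It holds on the text and needs no calculation.

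**Step 2: the possible data sources**

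- Historical genotypes: collected if available, not required for entry (protocol 6.2.1).
- Day 1 whole blood for HIV-1 DNA archive testing: mandatory for all participants in both arms (protocol 6.9.1).
- Post-baseline genotypes: confirmed rebound at 200 copies/mL or more (6.13.1). Under 6.13.2, those at or above 200 copies/mL "at study drug discontinuation, last visit, or Week 24 or Week 48 visit, will also have resistance testing conducted". This covers mostly viraemic participants.

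The first two do not depend on outcome; the third does in part.

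**Step 3: reproduce the planned power**

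Inputs from protocol 8.8: 320 and 160 participants, 4% in both arms, margin 0.06, Farrington-Manning score test, one-sided 0.025. The restricted estimates under a 6-point difference are 0.0794 and 0.0194.

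- Null SE: s0 = √(0.0794×0.9206/320 + 0.0194×0.9806/160) = 0.01865
- SE under equality: s1 = √(0.04×0.96/320 + 0.04×0.96/160) = 0.01897
- z = (0.06 − 1.96×0.01865)/0.01897 = 1.236, so power = 89.2%

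This matches the stated 89%. Full binomial enumeration gives 91.5% with actual alpha 0.026, matching the 91% and 0.026 in SAP Table 1-1.

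**Step 4: illustrative loss of participants**

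If a share e is lost from each arm, both SEs grow by 1/√(1−e), so z = 3.162×√(1−e) − 1.926.

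| e (assumed) | Arms | z | Power | Enumerated |
|---|---|---|---|---|
| 0 | 320/160 | 1.236 | 89.2% | 91.5% |
| 5% | 304/152 | 1.156 | 87.6% | 90.5% |
| 10% | 288/144 | 1.074 | 85.9% | 88.0% |
| 20% | 256/128 | 0.902 | 81.7% | 84.9% |

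Planned enrolment equals the powered 320/160, so nothing is held back for exclusions.

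**Step 5: illustrative removal of failures**

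Suppose the truth is 10% against 4%, exactly at the margin, and each failure is removed with probability f in both arms. The observed rate becomes p(1−f)/(1−pf). The table shows the apparent difference and the simulated chance of declaring non-inferiority (same test, at least 2,000,000 trials per row).

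| f (assumed) | B/F/TAF | SBR | Difference | False non-inferiority |
|---|---|---|---|---|
| 0 | 10.00% | 4.00% | 6.00 points | 2.6% |
| 5% | 9.55% | 3.81% | 5.74 points | 3.4% |
| 10% | 9.09% | 3.61% | 5.48 points | 4.4% |
| 20% | 8.16% | 3.23% | 4.94 points | 7.5% |

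Equal removal does not protect, because it shrinks an absolute difference that is judged against a fixed margin.

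**Step 6: condition (3)**

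The snapshot in 8.5.1.1 counts a stop for lack of efficacy as a failure even without RNA in the window. Condition (3) would drop such a participant if there was no on-treatment post-baseline result. For dropped non-events the effect is small and goes both ways: losing 3 to 10 from B/F/TAF, or 2 to 5 from SBR, moves the 2.6% to between 1.8% and 3.1%.

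**The case against.** A reader might infer that the FAS removes participants because they failed, and that the primary result is therefore biased towards non-inferiority. The documents do not support that.

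- The clause that counts mutations detected after baseline appears in the PP definition only. Its absence from the FAS definition suggests that such mutations were not meant to count there.
- A source that covers both arms and does not depend on outcome exists: the Day 1 archive sample.
- Genotyped participants and primary-endpoint failures are different groups. A failure at 50 to 199 copies/mL is not genotyped. A confirmed rebound at 200 or more before Week 24 is genotyped but counts as a success if suppressed in the window.
- The closest sponsor wording, SAP 3.1.2, is INSTI-only and historical. If that was the intent, condition (4) would remove mainly people already barred by inclusion criterion 5. That set does not govern Week 24, but it is evidence of intent.
- The SAP that governs Week 24 is not supplied and may already name the class and source.

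All of this stands, and it limits the point to the wording of the definition. It does not rescue that wording: the protocol does not say INSTI and does not say historical.

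Two further objections concern the figures. The removal shares in steps 4 and 5 have no basis in the documents, which is true. The planned decision rule is an exact 95% interval, not the score test. With the score test's critical value calibrated to exact size, the step 5 figures become about 2.4% with none removed and 3.2%, 4.2% and 7.1%, so the picture does not change.

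On condition (3), the snapshot has no clear category for someone who stops for a reason other than lack of efficacy before any post-baseline RNA. This matters only once condition (3) is deleted, because until then that person is outside the FAS.

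**Conclusion.** The definition is wrong as written and should be fixed. Condition (4) contradicts inclusion criterion 6, inverts the usual relation between FAS and PP set, and does not identify one population. That conclusion rests on the text alone.

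Its practical size is unknown, because no mutation prevalence is given. If the mutations come from a baseline source used alike in both arms, the arms need not be unbalanced, and the cost is representativeness and power: about 1.6 points at 5% excluded (89.2 − 87.6) and 7.5 points at 20% (89.2 − 81.7). Inflation of false non-inferiority to 3.4%, 4.4% or 7.5% needs the less likely reading in which post-baseline genotypes count, together with the assumed removal shares. Condition (3) is minor.

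The documents show a faulty definition. They do not show a biased primary result, and they do not show which definition was programmed.

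**What to change.** 1. Check the SAP that governs the Week 24 analysis first. If it already names the class and source, align the protocol with it.
2. Otherwise limit condition (4), in the protocol and in that SAP, to pre-existing INSTI resistance-associated mutations known from historical data, in line with SAP 3.1.2. State whether Day 1 archive DNA counts as a source and apply the answer identically in both arms. State that mutations found only on post-baseline samples remove nobody from the FAS. Anyone enrolled in breach of exclusion criterion 1 would then stay in the FAS and be removed from the PP set.
3. As a minor change, delete condition (3), and state in 8.5.1.1 how the snapshot classifies a participant who stops for a reason other than lack of efficacy before any post-baseline RNA.
4. The Week 24 analysis has already been run (SAP 2.1.1). If it used the protocol wording, report the primary result on both the set as run and the revised set, and label the revised one post hoc.

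The cost is a few lines of text and, at most, one re-run of the primary table. No new data collection is needed.
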